5.4.3.3 Abortions

A spontaneous abortion should be classified as a serious adverse event (as the Sponsor considers abortions to be medically significant), recorded on the Adverse Event eCRF, and reported to the Sponsor immediately (i.e., no more than 24 hours after learning of the event; see Section [5.4.2](#)).

If a therapeutic or elective abortion was performed because of an underlying maternal or embryofetal toxicity, the toxicity should be classified as a serious adverse event, recorded on the Adverse Event eCRF, and reported to the Sponsor immediately (i.e., no more than 24 hours after learning of the event; see Section [5.4.2](#)). A therapeutic or elective abortion performed for reasons other than an underlying maternal or embryofetal toxicity is not considered an adverse event.

All abortions should be reported as pregnancy outcomes on the paper Clinical Trial Pregnancy Reporting Form.

5.4.3.4 Congenital Anomalies/Birth Defects

Any congenital anomaly/birth defect in a child born to a female patient exposed to study drug or the female partner of a male patient exposed to study drug should be classified as a serious adverse event, recorded on the Adverse Event eCRF, and reported to the

Sponsor immediately (i.e., no more than 24 hours after learning of the event; see Section 5.4.2).

5.5 FOLLOW-UP OF PATIENTS AFTER ADVERSE EVENTS

5.5.1 Investigator Follow-Up

The investigator should follow each adverse event until the event has resolved to baseline grade or better, the event is assessed as stable by the investigator, the patient is lost to follow-up, or the patient withdraws consent. Every effort should be made to follow all serious adverse events considered to be related to study drug or trial-related procedures until a final outcome can be reported.

During the study period, resolution of adverse events (with dates) should be documented on the Adverse Event eCRF and in the patient's medical record to facilitate source data verification.

All pregnancies reported during the study should be followed until pregnancy outcome.

5.5.2 Sponsor Follow-Up

For serious adverse events, adverse events of special interest, and pregnancies, the Sponsor or a designee may follow up by telephone, fax, email, and/or a monitoring visit to obtain additional case details and outcome information (e.g., from hospital discharge summaries, consultant reports, autopsy reports) in order to perform an independent medical assessment of the reported case.

5.6 ADVERSE EVENTS THAT OCCUR AFTER THE ADVERSE EVENT REPORTING PERIOD

The Sponsor should be notified if the investigator becomes aware of any serious adverse event that occurs after the end of the adverse event reporting period (defined as greater than 5 months after the final dose of study drug), if the event is believed to be related to prior study drug treatment. These events should be reported through use of the Adverse Event eCRF. However, if the EDC system is not available, the investigator should report these events directly to the Sponsor or its designee, either by faxing or by scanning and emailing the paper Clinical Trial Serious Adverse Event/Adverse Event of Special Interest Reporting Form using the fax number or email address provided to investigators.

5.7 EXPEDITED REPORTING TO HEALTH AUTHORITIES, INVESTIGATORS, INSTITUTIONAL REVIEW BOARDS, AND ETHICS COMMITTEES

The Sponsor will promptly evaluate all serious adverse events and adverse events of special interest against cumulative product experience to identify and expeditiously communicate possible new safety findings to investigators, IRBs, ECs, and applicable health authorities based on applicable legislation.

To determine reporting requirements for single adverse event cases, the Sponsor will assess the expectedness of these events using the following reference document:

- RO7234292 Investigator's Brochure

The Sponsor will compare the severity of each event and the cumulative event frequency reported for the study with the severity and frequency reported in the applicable reference document.

Reporting requirements will also be based on the investigator's assessment of causality and seriousness, with allowance for upgrading by the Sponsor as needed.

6. STATISTICAL CONSIDERATIONS AND ANALYSIS PLAN

All patients enrolled prior to Version 4 of the protocol will not be included for any efficacy analysis. The safety data collected for these patients up to and including the end of treatment visit in Protocol BN40423 will be analyzed separately.

The primary efficacy analysis will be conducted at the end of the study (see Section 3.2). Treatment assignments will be unblinded to the Sponsor at the end of the study after the data have been cleaned and verified and the database has been locked.

Details of the planned statistical analyses mentioned below will be fully specified in a separate Statistical Analysis Plan (SAP), which will be finalized prior to the locking and unblinding of the study database.

Unless otherwise specified, all the p-values considered in Section 6 are two-sided.

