3. STUDY DESIGN

3.1 DESCRIPTION OF THE STUDY

3.1.1 Overview of Study Design

Study BN40423 is a Phase III, randomized, placebo-controlled, double-blind, multicenter clinical study to evaluate the efficacy, safety, PK, and biomarker effects of intrathecally administered RO7234292 in patients with manifest HD.

Prospective patients will undergo screening assessments during a 4-week screening period. A maximum of one re-screening will be allowed within 8 weeks of the initial screening failure for patients who fail the initial screening (see Section 4.5.1).

Upon completion of the screening period, eligible patients will be randomly allocated in a 1:1:1 ratio to receive RO7234292 Q8W (RO7234292 Q8W arm), RO7234292 Q16W (RO7234292 Q16W arm), or placebo Q8W (placebo arm) by IT injection, as described

in [Table 1](#). To maintain the study blind and integrity, patients in the RO7234292 Q16W arm will also receive placebo (i.e., alternating doses of active drug and placebo).

Table 1 Treatment Regimens after Implementation of Protocol Version 4

Arm	Treatment Regimen
RO7234292 Q8W arm	RO7234292 loading dose: 120 mg at Days 1 and 29 (2 doses) RO7234292: 120 mg Q8W from Week 13 to Week 93 (11 doses)
RO7234292 Q16W arm	RO7234292 loading dose: 120 mg at Days 1 and 29 (2 doses) RO7234292: 120 mg Q16W from Week 21 to Week 85 (5 doses) Placebo: Q16W from Week 13 to Week 93 (6 doses)
Placebo arm	Placebo: at Days 1 and 29 (2 doses) and Q8W from Week 13 to Week 93 (11 doses)

Q8W=every 8 weeks; Q16W=every 16 weeks.

During scheduled clinic visits, patients will undergo safety and tolerability evaluations that include neurologic examinations, vital signs, ECGs, clinical laboratory tests, MoCA, C-SSRS, neuroimaging assessments (neurologic safety sequences), and a review of any adverse events including related concomitant medications, as detailed in [Appendix 1](#).

If there is the occurrence of a failed IT bolus dosing procedure due to inadequate establishment of access to the IT space, a second dosing attempt may occur up to 7 days after the originally scheduled dosing visit. At this additional visit, safety and tolerability evaluations will be performed as described in [Appendix 1](#).

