Patients who choose to enroll in the OLE will complete an end-of-treatment visit in Study BN40423, which can also serve as the inclusion visit for Study BN40955. All patients who are prematurely discontinued by the Sponsor who choose not to consent to Study BN40955 will additionally undergo a 5-month postdose safety follow-up visit.

Table 2 presents the treatment regimen for all patients before implementation of the Version 4 protocol.

[figure not shown]
Table 2 *Treatment Regimens prior to Implementation of Protocol Version 4*

Arm	Treatment Regimen
RO7234292 Q4W arm	RO7234292: 120 mg Q4W from Week 1 to Week 97 (25 doses)
RO7234292 Q8W arm	RO7234292 loading dose: 120 mg at Days 1 and 29 (2 doses) Placebo: Q8W from Week 9 to Week 97 (12 doses) RO7234292: 120 mg Q8W from Week 13 to Week 93 (11 doses)
Placebo arm	Placebo: Q4W from Week 1 to Week 97 (25 doses)

Q4W=every 4 weeks; Q8W=every 8 weeks.

Figure 3 and Figure 4 present study schema and overviews of the dosing schedule, respectively. A schedule of activities is provided in Appendix 9, with additional assessments described in Appendix 10, Appendix 11, Appendix 12, and Appendix 13.

[figure not shown]
Figure 3 Study Schema for Patients Enrolled prior to Implementation of Protocol Version 4

EoT = end of treatment; HD = Huntington disease; Q4W = every 4 weeks; Q8W = every 8 weeks.

Notes: All patients who enroll prior to implementation of Protocol Version 4 will be prematurely discontinued from treatment by the Sponsor and offered treatment in the open-label extension study (BN40955). These patients will complete an EoT visit in Study BN40423, which can also serve as the screening visit for Study BN40955. All patients who are prematurely discontinued by the Sponsor who choose not to consent to Study BN40955 will additionally undergo a 5-month postdose safety follow-up visit. Patients in the Q8W arm will remain in the Q8W arm of the OLE study (BN40955). Patients in the placebo arm or Q4W arms will be randomly allocated to the Q8W or Q16W arms in Study BN40955.

Figure 4 Dosing Schema for Patients Enrolled prior to Implementation of Protocol Version 4

EoT = end of treatment; Q4W = every 4 weeks; Q8W = every 8 weeks.

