5.3.1 Adverse Event Reporting Period

Investigators will seek information on adverse events at each patient contact. All adverse events, whether reported by the patient or noted by study personnel, will be recorded in the patient's medical record and on the Adverse Event eCRF.

After informed consent has been obtained but prior to initiation of study drug, only serious adverse events caused by a protocol-mandated intervention (e.g., invasive
RO7234292—F. Hoffmann-La Roche Ltd
84/Protocol BN40423, Version 4

procedures such as biopsies, discontinuation of medications) should be reported (see Section 5.4.2 for instructions for reporting serious adverse events).

After initiation of study drug, all adverse events will be reported until 5 months after the final dose of study drug or until the patient receives his or her first dose in the OLE study (BN40955), at which time reporting will occur per the new study requirements.

Instructions for reporting adverse events that occur after the adverse event reporting period are provided in Section 5.6.

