6.7 SAFETY ANALYSES

The *safety* population (see Section 6.1) will be the primary population for all analyses of safety data. Incorrect treatment assignments (patients who received a treatment different than their planned randomized treatment) will be summarized and the impact on the safety assessment will be discussed.

For all safety analyses, patients enrolled prior to implementation of the Version 4 of the protocol will be summarized separately.

All verbatim adverse event terms will be mapped to MedDRA thesaurus terms. The adverse event severity grading scale indicated in [Table 4](#) will be used for assessing adverse event severity. Laboratory values determined as an adverse event should be graded as per [Appendix 5](#), which is based on the NCI CTCAE (v5.0).

All safety data, including adverse events, laboratory tests, CSSR-S, MoCA, ECG, and vital signs will be reported in individual listings and summarized by treatment for each assessment time using descriptive statistics. For continuous variables, both the original value as well as the change from baseline will be reported.

The incidence of adverse events will be summarized on the basis of body systems and dictionary preferred terms. The incidence of adverse events by severity and relationship to study drug or study procedure and incidence of marked abnormal laboratory test results will be provided.

The iDMC will review safety data throughout the study. Analyses required for the iDMC data review will be performed as described in the iDMC Charter.

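### As written, no stated safety analysis clearly covers what is collected after the end-of-treatment visit in patients enrolled before Version 4, the only cohort in this study with Q4W exposure

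*Protocol*

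**What the plan says.** **Analysis.** Section 6 keeps patients enrolled before Version 4 out of every efficacy analysis and says of their safety data: "The safety data collected for these patients up to and including the end of treatment visit in Protocol BN40423 will be analyzed separately". Section 6.1 limits the safety population to patients enrolled after Version 4. Section 6.7 says that for all safety analyses "patients enrolled prior to implementation of the Version 4 of the protocol will be summarized separately", and states no cut-off.

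**Collection.** Section 5.3.1 sets the reporting period once dosing has begun: "all adverse events will be reported until 5 months after the final dose of study drug". For anyone who enters BN40955 it closes sooner, when dosing there begins. Section 3.1.1.1 says that patients discontinued by the Sponsor who "choose not to consent to Study BN40955 will additionally undergo a 5-month postdose safety follow-up visit".

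**Regimens.** Table 2 (before Version 4) gives the Q4W arm as "RO7234292: 120 mg Q4W from Week 1 to Week 97 (25 doses" in all), next to a Q8W arm and a placebo arm. After Version 4 there is no Q4W arm: "eligible patients will be randomly allocated in a 1:1:1 ratio to receive RO7234292 Q8W (RO7234292 Q8W arm), RO7234292 Q16W (RO7234292 Q16W arm), or placebo Q8W".

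**The concern.** The protocol fixes an analysis window for this cohort that ends before its own collection period does. A safety visit provided specifically for part of the cohort falls outside the only window that Section 6 states for it. A statistical analysis plan that followed Section 6 to the letter would carry the gap forward.

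This matters because the cohort contains the most frequent dosing given in this study. Sections 1.3 and 3.3.1 report, from the Phase II extension, fewer adverse events, a smaller proportion of patients with moderate events, and fewer possibly drug-related events on Q8W than on Q4W. The pharmacological effect also outlasts a cut at about 4 weeks. Section 3.3.1 reports CSF mHTT still reduced by at least 35% in all five 120-mg patients sampled 8 weeks after the last dose. The weeks after the end-of-treatment visit are therefore not obviously free of drug effect, and they are the weeks whose analysis is left unstated.

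**Working it through.** There is no stated statistical figure to reproduce. The check sets the analysis sections against the collection sections and then measures the uncovered interval.

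**1. Which stated analysis could hold data after the end-of-treatment visit?**
- Section 6, opening: separate analysis of this cohort, window ending at that visit. Does not reach the later data.
- Section 6.1, safety population: patients enrolled after Version 4 only. Does not include the cohort.
- Section 6.7: cohort summarised separately, no window given. It neither repeats nor lifts the Section 6 limit.

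Section 6 is thus the only place that sets a window for this cohort, and none of the three clearly covers the later data.

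**2. What is collected after that visit, by patient group?**
- *Discontinued by the Sponsor, declines the extension* (Sections 3.1.1.1, 5.3.1): adverse events to 5 months after the last dose, plus the 5-month visit. All of this after the end-of-treatment visit is outside the stated window.
- *Discontinued by the Sponsor, enters the extension* (same sections): adverse events to the first extension dose. The end-of-treatment visit can double as the entry visit, so only the gap to that first dose is outside.
- *Stopped treatment earlier and stayed in the study* (Section 3.1.1.1; Appendix 9, footnote b): not eligible for the extension. The schedule gives an early-termination visit at 28 days (±3) after the last dose, visits at Weeks 53 and 69 if not already completed, and an end-of-treatment visit for early terminators at Week 101. If that last visit is the one Section 6 means, little or nothing may be outside.

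**3. How long is the uncovered interval for decliners?**

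Full pre-Version 4 schedule (Table 2; Appendix 9): last dose Week 97, end of treatment Week 101, safety follow-up Week 117.
- Collected after the last dose: 117 − 97 = 20 weeks.
- Inside the stated window: 101 − 97 = 4 weeks.
- Outside: 20 − 4 = 16 weeks; 16 / 20 = 80%.

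These patients are all to leave before Week 101, so the calendar weeks are illustrative. As a second route, assume the end-of-treatment visit falls 28 days (±3) after the last dose, as the early-termination visit does, and take 5 months as about 152 days.
- Visit at 28 days: 152 − 28 = 124 days; 124 / 152 = 82%.
- Visit at 31 days: 152 − 31 = 121 days; 121 / 152 = 80%.
- Visit at 25 days: 152 − 25 = 127 days; 127 / 152 = 84%.

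Both routes put about four fifths of the post-dose reporting period outside the stated window for this group.

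**4. How many patients or events?** The document gives neither the number enrolled before Version 4, nor the number on Q4W, nor the number who decline the extension. The loss cannot be expressed as a count.

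**The case against.** The strongest reply is that Section 6 nowhere says later data are discarded. Its sentence can be read as separating this cohort from the main analyses, and its BN40423 data from its extension data. Section 6.7, the operative safety section, has no cut-off and promises individual listings of all safety data. Full details are also left to the statistical analysis plan. This stands in part. A reader might infer that post-treatment data will be dropped, but the text does not support that; it shows only that no stated analysis clearly includes them. The reply does not remove the problem, because the protocol did not leave the window open. It named one, and that window is shorter than the collection period.

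A reader might also infer that the loss is worst in patients who stopped early for poor tolerability. The document does not support this. The 5-month visit in Section 3.1.1.1 is stated for Sponsor-discontinued patients who decline the extension, and earlier stoppers may be covered as far as Week 101. That decliners tolerated treatment worse is possible, but nothing in the document shows it. Nor is the cohort purely Q4W, so the affected data are not all Q4W data.

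Two further points on the other side are fair. Ongoing oversight does not depend on this sentence: adverse event reporting, expedited reporting and the unblinded reviews by the data monitoring committee continue. And data after the end-of-treatment visit come from a self-selected subset, so a common cut there keeps observation windows comparable. That argues for presenting the later events apart, not for leaving them without a stated analysis.

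**Conclusion.** The point holds as a mismatch between a stated analysis window and a stated collection period. It falls mainly on Sponsor-discontinued patients who decline the extension. For them about 80% of the post-dose reporting period lies beyond the window (80% to 84% across the assumptions shown). This rests on the end-of-treatment visit falling about 4 weeks after the last dose, which the document fixes for the early-termination visit but not explicitly for Sponsor-discontinued patients. For extension entrants the loss is limited to the interval before their first extension dose. For earlier stoppers it depends on which visit Section 6 means. The number of events at stake is unknown.

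The conclusion assumes that the statistical analysis plan, which is not at hand, follows the protocol sentence; it could widen the window. Efficacy analyses, sample size, type I error and the main safety population are not affected. The correction is worth making because it concerns the only Q4W exposure in this study and uses data already being collected.

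**What to change.** Replace the sentence in Section 6 with:

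*All safety data collected for these patients in Protocol BN40423 through the end of the adverse event reporting period (5 months after the final dose, or the first dose in BN40955 if earlier; Section 5.3.1), including the safety follow-up visit where performed, will be analyzed separately.*

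Give Section 6.7 the same window. Starting from all data collected, not from the first dose, keeps the pre-dose serious adverse events caused by protocol-mandated interventions that Section 5.3.1 collects. Tying the end to the reporting period, and not to a visit, also removes the doubt over which end-of-treatment visit applies to earlier stoppers.

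The cost is one sentence and a matching line in Section 6.7; no new data are needed. There is a small downside: follow-up after the end-of-treatment visit will be longer in decliners than in extension entrants. Events after that visit should therefore be shown separately from events up to it, by treatment arm, so that the unequal follow-up does not distort the comparison.

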6.1 ANALYSIS POPULATIONS

The intent-to-treat (ITT) population will consist of all patients *enrolled after implementation of Protocol Version 4* who received any study treatment. Randomized patients who receive incorrect therapy from that intended will be summarized in the group according to their planned randomized treatment. The ITT population will be the primary population for all analyses of primary and secondary efficacy variables.

The safety population for the trial will consist of all patients who enroll after implementation of Version 4 of the protocol and also receive any study treatment. The safety population will be the primary population for all safety analyses. For the purpose of all safety analyses, it will be assessed whether patients received a treatment different from the one they were randomized to at any time during the course of the study. In case the number and duration of such "treatment switches" warrants it, the safety population may be redefined by reallocating individual patients to the treatment actually received, as opposed to which treatment they were randomized to.

The PK population will include all randomized patients who received at least one dose, and had sufficient sampling to permit PK evaluation.

RO7234292—F. Hoffmann-La Roche Ltd

97/Protocol BN40423, Version 4

6.2 DETERMINATION OF SAMPLE SIZE

The planned sample size is adequate to capture meaningful clinical decline on both the TFC and cUHDRS and was estimated on the basis of data available from non-interventional studies (TRACK-HD, COHORT, ENROLL-HD) and a randomized placebo-controlled study (2CARE). Based on these data, using the anticipated trial population, a meta-analysis for the change from baseline at 24 months in TFC score suggested a natural decline of 1.36 points and a corresponding pooled standard deviation of 1.78. A *conservative treatment discontinuation rate at Week 101 for patients receiving placebo or active is assumed to be 20% and 15%, respectively. Using these assumptions, the simulation described below was performed to estimate the sample size.*

Description of Simulations to Derive the Sample Size

The design used for the simulation was simplified to consider only 2 treatment arms (placebo and active) and 2 postbaseline timepoints (Week 49 and Week 101). These simplifications are justifiable given that:

- *A hierarchical procedure will be used to test the primary endpoint for the two regimens against placebo, with the Q8W regimen tested first (see Section 6.3).*
- *The difference on the derived sample size for considering more than two postbaseline timepoints would be minimal.*

The following algorithm was run and repeated 500,000 times:

1. *Generate change from baseline values in TFC at Week 49 and Week 101 for N active patients according to the following bivariate normal distribution:*

$$\begin{pmatrix} y_{wk49} \\ y_{wk101} \end{pmatrix} \sim N \left(\mu = \begin{pmatrix} 0.47 \\ 0.82 \end{pmatrix}, \Sigma = \begin{pmatrix} 1.56^2 & 0 \\ 0 & 1.78^2 \end{pmatrix} \right)$$

where y_{wk49} and y_{wk101} is the change from baseline in TFC, respectively, at Week 49 and Week 101, μ is the assumed true change at those two timepoints, and Σ is the variance-covariance matrix. Subsequently:

- *set to missing, due to study drug-related (SDR) reasons, both values at Week 49 and Week 101 for 5% of the N patients. Set to missing, due to non-study drug-related (NSDR) reasons, both values at Week 49 and Week 101 for additional 2.5% of the N active patients.*
- *set to missing, due to SDR reasons, only the value at Week 101 for additional 5% of the N active patients. Set to missing, due to NSDR reasons, only the value at Week 101 for additional 2.5% of the N active patients.*

2. Generate change from baseline values in TFC at Week 49 and Week 101 for N placebo patients according to the following bivariate normal distribution:

$$\begin{pmatrix} y_{wk49} \\ y_{wk101} \end{pmatrix} = N \left(\mu = \begin{pmatrix} 0.79 \\ 1.36 \end{pmatrix}, \Sigma = \begin{pmatrix} 1.56^2 & 0 \\ 0 & 1.78^2 \end{pmatrix} \right)$$

where y_{wk49} and y_{wk101} is the change from baseline in TFC, respectively, at Week 49 and Week 101, μ is the assumed true change at those two timepoints, and Σ is the variance-covariance matrix. Subsequently:

- set to missing both values at Week 49 and Week 101 for 10% of the N placebo patients
- set to missing only the value at Week 101 for additional 10% of the N placebo patients

Given how missing data will be imputed, it is not relevant to differentiate missing data into SDR versus NSDR reasons for placebo patients.

3. Apply multiple imputations and derive 20 complete datasets. Missing data on placebo patients were imputed from the placebo arm. Missing data on active patients, depending on if due to NSDR or SDR reasons, were imputed respectively from the active or the placebo arm.
4. Use a t-test to compare active versus placebo at Week 101 for each completed dataset and pool the result (Rubin 1987) to derive an estimate of the treatment effect, including a p-value.

Across the 500,000 simulations, the power achieved, with the N patients per arm was calculated by dividing the number of times the p-value (in above Step 4) was below 5% by 500,000. The above procedure was repeated by only changing the N until the calculated power was close to 80%.

It was estimated that 220 patients per arm will provide approximately 80% power, at a two-sided $\alpha = 0.05$ level, to detect a 40% slowing of clinical decline for RO7234292 as compared with placebo at 101 weeks. This treatment effect translates into an expected average decline of ~0.82 points at 101 weeks for the RO7234292 arms. The minimal detectable difference with these assumptions is ~0.38 points.

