6.3 TESTING STRATEGY AND MULTIPLICITY ADJUSTMENT

A hierarchical approach will be used for multiple adjustments that accounts for comparisons of two active dosing regimens (RO7234292 Q8W and RO7234292 Q16W) versus placebo, as well as multiple endpoints (the primary and secondary endpoints).

The primary endpoint will be tested for RO7234292 Q8W against placebo at alpha level 5% and, if significant, then RO7234292 Q16W against placebo.

Secondary endpoints will be tested for each active treatment versus placebo. Within each testing chain (RO7234292 Q8W and RO7234292 Q16W), the endpoint will be tested only if the preceding endpoint is significant at the divided alpha level. Details of the order for secondary endpoints and the split of alpha will be detailed in the SAP.

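### The 80% power in Section 6.2 applies to the Q8W comparison only; at the same 40% slowing, power for Q16W under the hierarchy is about 69%, or about 64% if the Section 6.2 algorithm is run as written

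*Protocol*

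**What the plan says.** Section 6.2 describes the simulation behind the sample size: "The design used for the simulation was simplified to consider only 2 treatment arms (placebo and active) and 2 postbaseline timepoints". It calls this justifiable because the primary endpoint is tested hierarchically, with Q8W first. The result is: "It was estimated that 220 patients per arm will provide approximately 80% power", at a two-sided 5% level, "to detect a 40% slowing of clinical decline for RO7234292 as compared with placebo at 101 weeks". The next sentence gives the effect for both regimens together: "expected average decline of ~0.82 points at 101 weeks for the RO7234292 arms".

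Section 6.3 fixes the order of testing: "The primary endpoint will be tested for RO7234292 Q8W against placebo at alpha level 5% and, if significant, then RO7234292 Q16W against placebo". Section 6.6.2 makes the comparison of each active arm with placebo part of the primary efficacy analysis.

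The synopsis repeats the power and effect sentences. It mentions neither the two-arm simplification nor the test order, and says only that a suitable procedure will control the overall type I error.

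**The concern.** Under a fixed sequence, the power of the second comparison is the probability that both tests are significant. Testing Q8W first justifies a two-arm simulation for Q8W. It does not justify carrying that figure over to Q16W, whose claim depends on both tests. Because the power sentence names no regimen and the effect is stated for both arms, a reader can take 80% as applying to either regimen, most easily from the synopsis.

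Section 3.3.1 calls testing the less frequent regimen of high interest. If Q16W ends up untested or non-significant, reading that result against 80% power would overstate the evidence that the regimen does not work.

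**Working it through.** **Inputs**
- Placebo change and SD (Section 6.2): "a natural decline of 1.36 points and a corresponding pooled standard deviation of 1.78".
- Active decline 0.82 in both arms (Section 6.2), so the difference is 1.36 − 0.82 = 0.54 points; 40% of 1.36 is 0.544.
- 220 patients per arm (Section 6.2), allocated 1:1:1 (Section 3.1.1).
- Discontinuation (Section 6.2): "for patients receiving placebo or active is assumed to be 20% and 15%, respectively". The algorithm splits the active 15% into 10% study-drug-related, imputed from placebo, and 5% not study-drug-related, imputed from the active arm.
- Alpha 5% for the first test (Section 6.3); Section 6 states that "all the p-values considered in Section 6 are two-sided".
- Both active arms are compared with the same placebo arm (Section 6.6.1).

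**Step 1. The stated figure, by a simple formula**
- n per arm = 2 × (1.96 + 0.842)² × 1.78² / 0.54² = 170.6, so 171. Dividing by 0.80 gives 214, against 220 stated.
- With 0.80 × 220 = 176 evaluable per arm, SE = 1.78 × √(2/176) = 0.190. Power = Φ(0.54/0.190 − 1.96) = 81.2%.
- Minimal detectable difference = 1.96 × 0.190 = 0.37, against about 0.38 stated.

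On this calculation the stated 80% is reproduced for one active arm against placebo.

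**Step 2. Q16W under the hierarchy, taking 80% for each single test**
- Correlation of the two test statistics from the shared placebo arm: ρ = (1/nP) / (1/nP + 1/nA). This is 0.50 at 220:220 and 0.515 at 176:187 (20% and 15% missing).
- Joint power = Φ₂(z₀.₈₀, z₀.₈₀; ρ) = 68.7% at ρ = 0.50 and 68.9% at ρ = 0.515.
- Given success on Q8W, Q16W succeeds with probability 0.687 / 0.80 = 86%.

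**Step 3. The Section 6.2 algorithm as written, with a second active arm**

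Settings: 220 per arm, zero covariance between Week 49 and Week 101, the stated missing-data fractions and imputation sources, 20 imputations, Rubin pooling, and one shared placebo arm.
- Power of each single test: about 76%.
- Power for both: about 64%.
- Check: Φ₂ at 76% per test gives 63.3% (ρ = 0.50) to 63.5% (ρ = 0.515). Independence would give 0.76 × 0.76 = 58%, so the 64% already allows for the shared placebo arm.
- Imputing 10% of active patients from placebo shrinks the expected difference to about 0.90 × 0.54 = 0.49, a dilution that Step 1 leaves out.
- With an assumed within-patient correlation of 0.5 in place of zero, the figures are about 78% and 66%.

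**Step 4. A smaller Q16W effect (assumption, not in the protocol's sizing)**

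Take 30% slowing for Q16W, 0.30 × 1.36 = 0.408 points, with Q8W unchanged.
- On the Step 2 basis, the single-test power for Q16W is about 56% and the joint power 50% to 51%.
- On the Step 3 basis, they are about 51% and 45%.

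| Basis | Q8W | Q16W under the hierarchy, 40% slowing | Q16W, 30% slowing (assumed) |
|---|---|---|---|
| Stated 80% per test | 80% | 69% | about 50% |
| Section 6.2 algorithm as written | 76% | 64% | about 45% |

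**The case against.** Sizing a fixed-sequence trial on its first test is a legitimate choice, and the protocol nowhere requires 80% power for both regimens. Section 6.2 discloses the two-arm simplification and ties it to Q8W being tested first. The power sentence does not itself refer to both arms; the plural is in the following sentence and describes the assumed decline. Treatment differences with 95% confidence intervals will be derived for the primary analysis, which limits over-reading of a non-significant Q16W result. All of this stands. It makes the point one of incomplete reporting and leaves the design sound.

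Four stronger readings are tempting, and the documents do not support them.
- A reader might infer that the protocol claims 80% power for Q16W or for both regimens. It does not say so; it leaves the regimen unnamed and gives no second figure.
- A reader might infer that gatekeeping takes the stated 80% down to 64%. With a shared placebo arm it takes 80% to about 69%. The 64% belongs with 76% per test, and multiplying 0.8 by 0.8 would wrongly treat the two tests as independent.
- A reader might take any of these figures as the trial's actual chance of success. They describe an unadjusted t-test on TFC. The planned analysis is an ANCOVA, cUHDRS is the primary endpoint outside the FDA setting, and Section 6.6.1 uses observed off-treatment values after study-drug-related discontinuation where the simulation imputes them all from placebo.
- A reader might treat 45% to 50% as the protocol's implied Q16W power. The only 30% slowing in the document (Section 3.3.1) concerns trial duration. Applying it to Q16W is an assumption.

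**Conclusion.** The quoted power applies to the Q8W comparison, and Section 6.2 and the synopsis should say so. At equal 40% slowing, the power to declare Q16W is about 11 points below the stated 80% if each single test has 80% (80 − 69). It is about 12 points below the single-test figure if the algorithm is run as written (76 − 64). This rests on the protocol's TFC assumptions, equal effects in the two active arms, and a correlation near 0.5 from the shared placebo arm. The 76% and 64% also depend on how the algorithm's imputation step is rebuilt; they rise to 78% and 66% under an assumed within-patient correlation of 0.5. The case for stating the Q16W figure is the same on either basis.

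**What to change.** In Section 6.2 and the synopsis, state that the quoted power applies to the Q8W comparison only. Re-run the simulation with three arms sharing one placebo group, and report the power to declare Q16W under the hierarchy beside the Q8W power. Take both figures from the same run: 80% goes with about 69%, and 76% with about 64%. Do not print 80% beside 64%. A figure for a smaller Q16W effect, such as 30% slowing (about 45% to 50%), may be added if it is labelled as an assumption.

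Sample size, alpha and test order stay as they are. The cost is one simulation, a sentence in two places, and a less favourable stated figure for Q16W.
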